**Table 3: Comprehensive Acne Severity Scale (CASS)**

GRADE*		DESCRIPTION
Clear	0	No lesions to barely noticeable ones. Very few scattered comedones and papules.
Almost clear	1	Hardly visible from 2.5 metre away. A few scattered comedones, few small papules and very few pustules.
Mild	2	Easily recognisable; less than half of the affected area is involved. Many comedones, papules and pustules.
Moderate	3	More than half of the affected area is involved. Numerous comedones, papules and pustules.
Severe	4	Entire area is involved. Covered with comedones, numerous pustules and papules, a few nodules and cyst.
Very severe	5	Highly inflammatory acne covering the affected area, with nodules and cyst present.

Inspection is done at a distance of 2.5 meters away for acne on face, chest and back.

▪ **Chest area defined as:**

Anterior torso superiorly defined by suprasternal notch extending laterally to shoulders and inferiorly by a horizontal line defined by the xiphoid process.

▪ **Back area defined as:**

(Is demarcated by the) superior aspects of the shoulders extending to the neck and inferiorly by the costal margins.

- The participants will be treated with once weekly isotretinoin at a dosage of 1-1.5mg/kg/week. Exact dosage will be determined by the provider.
- Efficacy will be determined by having one trained individual (“Photo Reviewer”) grade patients’ facial photographs to limit interrater reliability bias. This person will not be told what is being used as the study drug, and will not be told any details of the study, including that all participants are on the study drug, in order to limit observer bias (blinded). Every month, clinical photos will be submitted for each patient enrolled in the study. The participants will have these photos taken at monthly follow-up visits (monthly follow-up visits are standard of care per requirements of IPLEDGE, the medication monitoring system for isotretinoin). For in-person visits, these monthly photos will be taken by the provider or staff in clinic and directly uploaded to the Epic electronic medical record. For any virtual clinic visits (given the COVID-19 pandemic), the monthly photos will be submitted into MyChart by the patient.

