- The Study Coordinator (Dermatology research fellow), who per the study consent form has permission to access participants’ medical records for the purpose of the study, will follow each patient through Epic electronic medical record to confirm that photos are submitted in a timely manner.
- A separately trained individual (“Data Retriever”), who per the study consent form has permission to access participants’ medical records for the purpose of the study, will submit any uploaded photos (baseline and at the end of each

month) from Epic to the Photo Reviewer by secure, encrypted email, labeling only with participant number and date of photo. This ensures that the Photo Reviewer is always reviewing only individual photos and will not ever enter the patient's medical chart to further limit bias.

- Photo Reviewer will receive photos and document a monthly CASS grade for each participant (in encrypted Excel only accessible by study team members, using study participant numbers without patient identifiers, **attachment F**). Baseline photos will all be a grade 3 (moderate) based on study inclusion criteria. "Improvement" is defined as decrease in grade from a 3 (moderate) to either a 2 (mild), 1 (almost clear), or 0 (clear). "Failure" is defined as showing no improvement (remaining a grade 3), increasing grade of 4 (severe) or 5 (very severe), or requiring additional oral treatment (for example, worsening acne requiring conventional dose isotretinoin). Treatment success can then be calculated as the percentage of participants with improvement out of the total number of participants at the end of four months, in addition to treatment success after each month of treatment.
- Any participants who take any oral tetracycline antibiotics or trimethoprim-sulfamethoxazole during the study period (for a reason besides acne) will be removed from the study in order to prevent any confounding. Patients requiring these medications for acne after the study period has begun will remain included in the study and will be listed as intervention "failure" as above. Participants will be allowed to continue use of topical acne cleansers and treatments during the study as per standard of care.

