- Pregnancy test data will be collected from the medical record as these will be performed as part of the clinical care of the patient. Female participant's individual providers will order pregnancy tests, which per standard of care are typically collected at baseline x 2 (one month apart), every month while on the medication, and at least one month after stopping the medication. If patients have any significant laboratory abnormalities that could be related to the medication, the medication will be discontinued.
- The Study Coordinator (Dermatology research fellow) will follow each patient through Epic electronic medical record to confirm that laboratory work and surveys are completed in a timely manner.
- Data Retriever will follow each participant's laboratory blood work and any abnormalities will be entered into the encrypted Excel sheet; this individual will also enter all survey responses into the same encrypted Excel sheet (attachment F).

To determine patient satisfaction (secondary endpoint), the Dermatology Life Quality Index (<https://www.cardiff.ac.uk/medicine/resources/quality-of-life-questionnaires/dermatology-life-quality-index>) will be administered at baseline before receiving any medication and at each monthly follow-up visit. The DLQI is the most frequently used validated, patient-reported outcome measure in dermatology trials (attachment B). License for use of survey has been obtained (attachment H).

- Data Retriever will follow each participant's surveys and enter information into the same encrypted Excel sheet as noted above.

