## 12.0 Data Management

- Participant clinical photos, signed consent form, and photos or scans of their completed surveys will be uploaded into the Media tab of Epic electronic health record either in clinic or by the patient through MyChart. Laboratory result information will result in the patient's Epic medical chart. This will keep this information secure and protected. Study team members will have permission to access study participants' medical records for the purpose of retrieving information for the study, as listed in the study consent form.
- Data Retriever will securely email ("send secure") the participant photos (deidentified) to the Photo Reviewer to score. This will occur over MUSC email only.
- Storing of synthesized study information (participant follow-up dates, scoring of clinical photos, list of any participant lab abnormalities, participant survey answers) will be entered in an encrypted Excel sheet, labeled only with participant number and without patient identifiers (**attachment F**). Only investigators directly involved with the study will have access to this encrypted Excel sheet.
- Paper consent forms will be stored in a locked office (Rutledge Tower, dermatology office floor 10). Electronic consent forms will be stored on a MUSC desktop computer that is secured by username and password. Photos of all consent forms will be taken for upload into patient's Media tab in their medical chart.
- Since this is a proof-of-concept study, there will not be any statistical analysis. Observations will be reported.
- Data will not leave MUSC.

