### **13.0 Provisions to Monitor the Data to Ensure the Safety of Subjects (if applicable)**

- Data Retriever (as above), the Principal Investigator, and the Study Coordinator will serve as a data monitoring committee. At the end of each month, Data Retriever will review each participant's laboratory blood work results and surveys and input the information into the encrypted Excel sheet. This Excel sheet will be reviewed by the rest of the data monitoring committee. The clinicians that see each participant will also review laboratory blood work as it is completed and are instructed to notify the investigators with any significant abnormalities as they arise. Any pertinent abnormalities (elevated liver enzymes, elevated triglycerides) will be discussed with the patient by their individual providers and the decision to continue or discontinue isotretinoin will be a joint patient-provider decision made at that visit based on clinical judgement. Additionally, any clinically significant baseline laboratory abnormalities will exclude the patient from enrolling in the study. If the patient's liver enzymes or triglycerides increase to > 3 times the upper limit of normal during the study period, the medication will be stopped.

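### The blinded Photo Reviewer records grades in the same workbook that holds side-effect, laboratory and quality-of-life data, with no stated separation of access, so the data flow as written does not protect the blinding

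*Protocol*

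**What the plan says.** Three strands of the Protocol bear on this.

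**The blinding.** Section 10.0 makes one trained person, the Photo Reviewer (a medical student), the grader of facial photographs on the Comprehensive Acne Severity Scale (CASS). To limit observer bias this person is not told the study drug and "will not be told any details of the study, including that all participants are on the study drug". The same section adds that the reviewer works from individual photos and stays out of the medical chart.

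**Where the grades go.** Still in Section 10.0: "Photo Reviewer will receive photos and document a monthly CASS grade for each participant (in encrypted Excel only accessible by study team members". The file is identified as attachment F and is organised by participant number.

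**What else goes there.** Section 10.0 has the Data Retriever follow each participant's laboratory results, and "any abnormalities will be entered into the encrypted Excel sheet". For the surveys, "this individual will also enter all survey responses into the same encrypted Excel sheet (attachment F"; the Dermatology Life Quality Index (DLQI) answers are sent to the same file a few lines later. Section 12.0 describes one file in which follow-up dates, "scoring of clinical photos, list of any participant lab abnormalities, participant survey answers) will be entered in an encrypted Excel sheet", again attachment F. On access, Section 12.0 says only: "Only investigators directly involved with the study will have access to this encrypted Excel sheet". Section 13.0 shows that the entries are made at the end of each month, when the Data Retriever is to "input the information into the encrypted Excel sheet. This Excel sheet will be reviewed by the rest of the data monitoring committee".

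**The concern.** The study has a single open-label arm, so there is no comparison group to absorb a lenient reader. The only safeguard that the Protocol offers against observer bias in the efficacy grade is that the reader knows nothing about treatment. To enter a grade as instructed, that reader has to use a file that also receives survey answers about potential isotretinoin side effects (Section 10.0 lists dry skin, lips and eyes, night vision, mood and others, with severity), laboratory abnormalities and DLQI answers. Someone who sees such entries for every participant could work out which drug is in use and that nobody is untreated. Those are the two facts that the Protocol sets out to withhold.

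A drop of one grade, from 3 to 2, is enough for a participant to count as improved. Modest leniency in a borderline photograph can therefore change the classification, and the resulting success percentage is what the study will report. Section 16.0 looks to that result as a possible basis for larger randomised studies.

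**Working it through.** The Protocol states no figure on this point, so there is none to reproduce. The check is a trace of every mention of the workbook against the blinding statements.

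| Item | Where it is stored | Source |
|---|---|---|
| Monthly CASS grades, entered by the Photo Reviewer | Attachment F | Section 10.0 |
| Laboratory abnormalities, entered by the Data Retriever | Attachment F | Sections 10.0, 12.0, 13.0 |
| Side-effect survey answers | Attachment F | Sections 10.0, 12.0, 13.0 |
| DLQI answers | Attachment F | Sections 10.0, 12.0 |
| Follow-up dates | Attachment F | Section 12.0 |

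1. *Same file?* Yes. Section 10.0 calls it the same sheet for the surveys and again for the DLQI, and Section 12.0 lists all the contents together.
2. *Same key?* Yes. The workbook uses participant numbers, and the emailed photos carry the participant number and date. A photo can be matched to its row.
3. *Same period?* Yes. Section 13.0 has survey and laboratory data added monthly, while grading is under way.
4. *Any separation by role?* None is stated. Access is set for the sheet as a whole, with no tab, column or staged-entry restriction.
5. *Consequence.* If the Photo Reviewer has access, the side-effect and laboratory data are within reach. If not, the reviewer cannot enter grades as Section 10.0 requires. The text needs correcting in either case.

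**Number of grades exposed.** The inputs are a target of 50 and a minimum of 30 participants (Section 6.0), and four monthly post-baseline grades (Section 10.0).

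- Target: 50 × 4 = 200 post-baseline grades, of which 50 are at month 4.
- Minimum: 30 × 4 = 120 post-baseline grades, of which 30 are at month 4.

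Baseline grades are left out because the Protocol takes them all to be grade 3 and no on-treatment data exist at that time. The counts are upper limits: they assume that every participant is graded at every month and that the reader can see the other entries each time.

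**Size of the bias.** It cannot be computed. The Protocol gives no expected success rate, no reader agreement figure and no basis for estimating how far an unblinded reader would shift.

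**The case against.** **Attachment F is not shown.** It may have protected tabs or columns. This is fair. A reader might infer that the blinding is actually broken, and the documents do not support that. They support only that it is unprotected as written, because the text describes one shared sheet and no separation.

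**Earlier grades and time order are visible anyway.** One person grades every month from photos labelled with number and date, so the reader can order a participant's photos and link earlier grades without opening the workbook. This stands. That part of the exposure comes from the photo labels, and a separate form alone would not remove it. The side-effect, laboratory and DLQI exposure does come from the workbook, and relabelling photos would not close it.

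**Direction of bias.** A reader might infer that seeing earlier grades pushes results towards improvement. The documents do not support this. Everyone starts at grade 3, so anchoring on the earlier grade would pull towards no change, which counts as failure. Only inferring treatment plausibly favours improvement, and the two effects could partly offset each other.

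**The grade is not the whole endpoint.** Needing additional oral treatment also counts as failure, whatever the photo shows. This is correct. The grade still decides improvement for everyone else.

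**It is a proof-of-concept study.** Section 12.0 plans no statistical analysis and there is no between-arm contrast to distort. That limits the consequences, but the Protocol itself chose blinding to limit observer bias, and its data flow should be consistent with that choice.

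**Conclusion.** The point holds as a conflict within the Protocol. Section 10.0 promises a reader who knows nothing about treatment. Sections 10.0, 12.0 and 13.0 then place that reader's grades in a workbook filled monthly with side-effect, laboratory and DLQI data under the same participant numbers, without any stated limit on what the reader can see. The reader could infer the drug and that all participants are treated.

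Up to 200 post-baseline grades are exposed at the target of 50 participants, 50 of them at month 4. This rests on full follow-up and on attachment F having no restrictions beyond those in the text. It counts grades at risk, not grades shown to be wrong. A reader might want to attach a percentage-point inflation to the success rate, but any such figure would need assumed failure and misgrading rates that the Protocol does not supply.

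It is worth settling before grading starts, because blinding cannot be restored to grades already recorded with the workbook open.

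**What to change.** Amend Sections 10.0 and 12.0 as follows.

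1. The Photo Reviewer records grades on a separate form that holds only a photo code and a CASS grade.
2. The Data Retriever keeps the code list and merges the grades into attachment F.
3. The Photo Reviewer has no access to attachment F until all grading is locked. The access rule in Section 12.0 should say so explicitly.
4. Photos are sent under the code, without participant number or date, and in random order where timing allows. Within a monthly batch the order can be shuffled across participants. Shuffling across months would mean holding photos back and grading them together.

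Items 1 to 3 close the exposure through the workbook. Item 4 deals with time order and linkage to earlier grades. It weakens that linkage but does not abolish it, because faces remain recognisable.

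The cost is one extra spreadsheet, a coding and merging step by existing staff, and a wording amendment. No additional visits or personnel are needed.

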## **8.0 Recruitment Methods**

- Recruitment will occur during standard of care visits to the Dermatology Clinics including its virtual visits.
- The first person to inform eligible patients about the study will be a clinician directly involved in the eligible patient's care. The clinician will first determine if the patient may meet criteria (score of 3, moderate acne, on CASS clinical scale as described in more detail in section 10.0). If the patient expresses interest in the study, the clinician or study co-investigators will approach the patient without coercion and with the emphasis on the voluntary aspect of being enrolled in this study. He/she will also be told in a caring manner that no matter his/her decision, it will not affect his/her care. This discussion will take place either in-person during the patient's clinic appointment or over telephone within one business day of the appointment.
- If the discussion takes place in-person during the clinic appointment, the patient will be provided a printed recruitment pamphlet reiterating the information regarding the study (**attachment A**). Eligible patients who agree to participate will sign the study consent form. Weight will be obtained. A baseline photograph will be taken and uploaded into the patient's medical chart (Epic). Two baseline surveys (Dermatology Life Quality Index survey to assess patient satisfaction and a second survey regarding potential isotretinoin adverse effects) will be completed by the patient (**attachments B and C, respectively**). The patient's clinician will then counsel the patient on isotretinoin and IPLEDGE and enroll the patient in the IPLEDGE system following all prompts. The clinician will order baseline laboratory blood work (all patients) and

urinary pregnancy test (females). Once blood work has returned and is without any clinically significant abnormalities (see section 13.0), the weekly isotretinoin (at dose 1-1.5 mg/kg per week) will be prescribed by the clinician (for males). Females will need to wait an additional month to have a second negative pregnancy test before starting the medication per IPLEDGE standard of care. After a second negative pregnancy test at next monthly visit, the clinician can prescribe the weekly dosed isotretinoin.

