## 10.0 Study Design / Methods

This will be an open-label, prospective, proof-of-concept study of patients with moderate inflammatory acne. The patients will be treated for at least 4 months.

- The initial acne assessment will be performed by dermatologists and dermatology residents using a validated, clinical grading system (Comprehensive Acne Severity Scale, CASS as below) with lesion counts (inflammatory and noninflammatory). Only moderate acne patients who are eligible for enrollment will be allowed to participate. Recruitment methods are outlined in above section 8.0. A baseline photo will be taken and placed in the patient's medical chart (Epic).

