- Photo Reviewer will be a blinded medical student because all of the dermatology residents will be participating in the clinical care of study participants. The Photo Reviewer will be trained by the Primary Investigator (Dermatology Resident) and Study Coordinator (Dermatology Research Fellow) on how to use the objective CASS grading system.
- Data Retriever will be a Dermatology resident who will be trained by the Primary Investigator (Dermatology Resident) and Study Coordinator (Dermatology Research Fellow).
- All participants, regardless of whether they show "improvement" or "failure," will be followed for up to four months after the study period to assess for recurrence of acne. During this period, any further treatment decisions will be made by the patient and his or her clinician. Any participants who choose to continue once weekly isotretinoin will be asked to upload clinical photos and patient satisfaction surveys monthly through MyChart. Other participants who discontinue the isotretinoin will be asked about their follow-up acne treatment.

To determine patient adverse effects (secondary endpoint), we will monitor for side-effects of the interventional medication.

- Per standard of care, patients will be enrolled in IPLEDGE, requiring extensive counseling before starting the isotretinoin medication, monthly follow-up visits for males and females, and monthly urine pregnancy tests for females.
- Each patient will fill out a survey at baseline (**attachment C**) and at each monthly visit (**attachment G**) inquiring about potential side-effects of isotretinoin (with severity) including dry skin, dry mucous membranes (lips,

eyes), GI upset, bone or muscle pain, night vision abnormalities, mood swings/depression, headaches, delayed wound healing. If the follow-up visit between the patient and his or her clinician is virtual, the attached surveys will be sent in an encrypted email for completion by the participant. Photos of each completed survey will be uploaded into the patient's chart either at their clinic visit or by the patient via MyChart (virtual visit).

- Per standard of care, laboratory blood work (CBC, CMP, lipid panel) will be obtained prior to starting the medication and will be repeated two months into the study period (after two clinical follow-up visits, also per standard of care and confirmed by PRA), or more frequently if clinically indicated. The results will be reviewed from the medical record.

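### Improvement is measured from a baseline grade of 3 assigned by clinicians, but follow-up is graded by a different reader whose own baseline grade is not used

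*Protocol*

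**What the plan says.** Section 8.0 sets the entry requirement as a "score of 3, moderate acne, on CASS clinical scale", judged by the patient's clinician. Section 10.0 confirms who does this: "The initial acne assessment will be performed by dermatologists and dermatology residents using a validated, clinical grading system". The legend of the CASS table reproduced there reads: "Inspection is done at a distance of 2.5 meters away for acne on face, chest and back".

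Efficacy is graded by someone else. Section 10.0 has one trained person grade "facial photographs to limit interrater reliability bias", and specifies that the "Photo Reviewer will be a blinded medical student because all of the dermatology residents will be participating in the clinical care". This reader is trained on CASS by the Primary Investigator and the Study Coordinator. The reader receives the baseline photo and each month's photo, with "labeling only with participant number and date of photo", and records a monthly grade.

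The starting value for the comparison is then fixed: "Baseline photos will all be a grade 3 (moderate) based on study inclusion criteria". That value follows from eligibility and not from a reading of the photo. A participant counts as improved if a later grade is 2, 1 or 0. Failure is a grade of 3, 4 or 5, or a need for additional oral treatment. The primary result is the percentage improved at four months.

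**The concern.** The two ends of the comparison come from different raters and different material: a clinician's assessment at entry and a student's reading of a facial photograph afterwards. If the entry grade takes in the chest and back, as the table legend suggests, the body area differs too.

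The reader may well grade the baseline photo, but the definition neither requires nor uses that grade. No rule covers a baseline that the reader would not call 3. Using one reader limits variation between participants and across months 1 to 4. It does nothing for the step from baseline to follow-up, which is the step that defines success.

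This is the primary endpoint of a single-arm study, so no comparator would carry the same offset. Section 12.0 plans no statistical analysis, so no test result is at risk. At stake is the one efficacy percentage that Section 16.0 links to possible larger randomized studies.

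**Working it through.** **Inputs from the protocol.** Target enrolment is 50 (Section 6.0). The baseline is fixed at 3 and improvement means a follow-up grade of 2 or lower (Section 10.0). The protocol states no reader agreement, offset, severity spread or expected success rate, so there is no plan figure to reproduce. Everything below is illustration under assumed values.

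**Step 1: arithmetic without reading error.** Let q be the share the reader would grade 2 at baseline, r the share the reader would grade 4, and p the true rate of one-grade improvement. Those read as 2 count as improved whatever happens. Those read as 4 fail even after a one-grade fall. Hence

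reported rate = q + (1 − q − r) × p

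- q = 5/50 = 0.10, r = 0, p = 0: 0.10 + 0.90 × 0 = 10% for an inert drug.
- q = 0.10, r = 0, p = 0.5: 0.10 + 0.90 × 0.5 = 55%.
- q = 0, r = 0.10, p = 0.5: 0 + 0.90 × 0.5 = 45%.

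The distortion can go either way.

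**Step 2: simulation with reading error.** Assumptions: latent severity is normal with mean 2.5 or 3 and SD 0.8 or 1. Clinician, reader-baseline and reader-follow-up errors are independent, with SD 0.25 or 0.4. The reader's offset from the clinicians is 0, −0.25 or +0.25 grade. Values are rounded to CASS 0 to 5, and a participant is enrolled if the clinician's grade is 3. That makes 8 settings at each of 3 offsets, with 2 million patients per setting before the entry filter. Added oral treatment is not modelled. The present rule is follow-up grade ≤ 2; the own-baseline rule is follow-up grade below the reader's baseline grade. Ranges run over the 8 settings.

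| True effect | Present rule, no offset | Reader ¼ grade lower | Reader ¼ grade higher | Own-baseline rule, all three offsets |
|---|---|---|---|---|
| Inert | 13–27% | 29–43% | 4–15% | 14–22% |
| 30% fall one grade | 35–45% | 49–58% | 24–33% | 35–39% |
| 50% fall one grade | 50–57% | 62–68% | 38–45% | 50% |
| 80% fall one grade | 68–77% | 78–85% | 55–64% | 67–72% |
| 80% fall two grades | 83–85% | 86–89% | 81–82% | 83–84% |

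**Step 3: sensitivity to the offset.** Within a setting, going from a quarter grade low to a quarter grade high moves the present rule by 21 to 30 points for the inert and one-grade rows, and by 5 to 6 points for the two-grade row. The own-baseline rule moves by at most 1 point. At a true 50% one-grade rate, the present rule reports between 0.376 × 50 ≈ 19 and 0.681 × 50 ≈ 34 successes out of 50, depending on setting and offset.

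**Step 4: how often the stated baseline would be wrong.** With no offset at all, the reader's baseline differs from 3 in 25 to 41% of participants in these settings (2 or lower in 13 to 27%, 4 or higher in 9 to 20%).

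**The case against.** The strongest reply is that the remedy swaps a possible bias for a certain attenuation. Own-baseline scoring uses two error-prone readings. With no offset and a true 80% one-grade rate, it gives 67 to 72% against 68 to 77% under the present rule: lower in every setting, by up to about 7 points. With no offset, an inert drug and mean severity 3, it also gives slightly more false improvement. This stands: own-baseline scoring removes the offset, not the random error. It is a reason to report both results, but not to keep a baseline that the reader never supplied.

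The present rule can also be read as a fixed threshold, grade 2 or lower at month 4, applied by one person to everyone. That is a usable endpoint, but it measures severity at month 4, whereas the protocol presents it as a decrease from 3. Own-baseline scoring has its own oddity: a fall from 5 to 4 counts as improvement.

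The protocol does train the reader on CASS and withholds all study details. Training should narrow an offset, but nothing checks that it has. Withholding the details makes the dated labels less damaging, but the order of the photos remains visible.

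Finally, the mention of chest and back is a legend to a reproduced table, and no text says that a patient may enter on truncal acne alone. The mismatch in body area is therefore possible but not established. The data sheet (attachment F) is not shown and may hold a reader baseline grade; the definition would still not use it.

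**Conclusion.** The concern holds. The definition of success compares a clinician's entry grade with a different reader's follow-up grade, so the single-reader design does not protect the comparison that matters. The text alone establishes this.

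The size rests on assumed offsets, reading errors and severity spread. A quarter-grade offset in either direction could move the reported rate by tens of points between the two extremes if the drug is inert or responses are mostly one grade. It matters little if most participants improve by two grades. The direction is unknown. No formal decision is affected. The matter should be fixed because it bears on the only efficacy figure and the correction is cheap.

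**What to change.** In Section 10.0:

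- Delete the sentence that assigns grade 3 to all baseline photos, and require the Photo Reviewer to grade each baseline photo without being told what it should be.
- Label photos with a code that shows neither participant number nor date, and send them in mixed order. Faces may still be recognised as the same person, but the baseline photo will no longer be marked as such.
- Define improvement as at least one grade below the reviewer's own baseline. Define failure as the same or a worse grade, or added oral treatment as now.
- Report how many participants have a reviewer baseline other than 3, and give the result under the present definition (follow-up grade 2 or lower) alongside.

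The cost is a few sentences of protocol text, since baseline photos already go to the reviewer. The Data Retriever must keep a code key and link the grades back, and mixed batches replace the monthly dispatch. Section 17.0 withholds response results from participants until analysis, so nothing promised to them is delayed. The price in the results is that some baselines will not be 3, the success rate may look less favourable, and random reading error and regression to the mean remain.
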